20.2.4 Change in HbA1c levels at Weeks 12 and 24 from baseline

| Population: | FAS and PPS |
|-----------------|-----------------|
| Stratification: | Table: By visit |

Listing: by subject

Statistics: The actual and change from baseline data of HbA1c levels will be summarised as (n, mean, standard deviation, standard error, median, minimum, maximum and number with missing values).

The change from baseline variable and the missing HbA1c results imputation i.e. LOCF will be done by using derivations mentioned in section 20.1.4 and the efficacy tables will be presented for with and without imputed values separately for each population set.

The change in HbA1c level from baseline to Week 12 and baseline to week 24 will be analysed using the general linear model.

The change from baseline in HbA1c level as dependent variable and the baseline value of HbA1c as covariate.

The estimate, 95% confidence interval and p-value will be summarised for efficacy table.

The regression line for the general linear model without categorical variable is as follows:

 $Y = \alpha + \beta (X)$

Where,

Y= The response change in HbA1c levels.

 $\alpha = Intercept$

 β =slope

X= Covariate i.e. Baseline HbA1c results

The hypothesis is as follows

H0: $\beta = 0$

i.e. There is no statistically significant change in HbA1c levels at week 12 and 24 from baseline depending on the baseline HbA1c.

V/s

H1: β ≠ 0

i.e. There is statistically significant change in HbA1c levels at week 12 and 24 from baseline depending on the baseline HbA1c.

The above hypothesis will be tested based on α (alpha)=0.05, if the p-value ≥ 0.05 then we will conclude that there is no statistically significant change in HbA1c levels at week 12 and 24 from baseline i.e. Ho is accepted.

The sample SAS programme is as follows:

proc mixed data=dataset;

model Y= X / s cl;

estimate "Model with Mean baseline HbA1C" int 1 HbA1c_baseline mean /CL;

ods output estimates=output dataset;

run; quit;

The listing of the HbA1c data will be provided containing the additional variable for identification of the HbA1C results measured after intake of rescue medication.

20.2.5 Percentage of subjects reaching HbA1c targets ≤6.5% and <7% at week 24

| Population: | FAS and PPS | |
|-----------------|--|--|
| Stratification: | Table: NA | |
| | Listing: NA | |
| Statistics: | Subjects reaching HbA1c levels of ≤6.5% and <7% at Week 24 will be identified as derivation mentioned in section 20.1.5. | |
| | | |
| | we will analyse this endpoint descriptively as binary variable. | |
| | Binary variable is as follows, | |
| | Response=1, if HbA1c (%) meets target level | |
| | Response=0, if HbA1c (%) does not meets target level | |

The HbA1c values used to calculate this binary variable will be the LOCF value, that is, in case the Week 24 value is missing, the Week 12 value will be used. Subject with missing HbA1c data at Week 12 and Week 24 will be considered as not having reached the target (i.e. response =0 for binary variable).

This endpoint will be summarised for subject reaching the HBA1c target level for both cases as number and percentage (n and %) at week 24.

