### 10.3. Statistical Analyses

#### 10.3.1. General Statistical Considerations

All data will be entered, verified, and archived by a contract research organization (CRO) external to Lilly and/or at Lilly. Data listings, summaries, and analyses will be performed by a CRO under the guidance and approval of statisticians at Lilly. Statistical analysis of this study will be the responsibility of Lilly.

Any change to the data-analysis methods described in the protocol will require an amendment ONLY if it changes a principal feature of the protocol. Any other change to the data analysis methods described in the protocol, and the justification for making the change, will be described in the statistical analysis plan and/or in the clinical study report. Additional exploratory analyses will be conducted as deemed appropriate.

Safety and efficacy analyses will be conducted on the full analysis set (FAS) or safety set. These sets include all data from all enrolled subjects who take at least 1 dose of study treatment.

All tests of treatment effects will be conducted at a 2-sided alpha level of 0.05, unless otherwise stated.

The planned statistical method for the primary analysis is the calculation of the estimate and the 95% confidence interval for the incidence of total (symptomatic or asymptomatic with FBG level  $\leq 54$  mg/dL [3.0 mmol/L]) hypoglycemic events at Week 24.

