7.4 Statistical tests

This is the single arm study so no comparison tests will be performed.

The incidence of hypoglycemia will be analysed using the exact binomial method (Clopper-Pearson method) for single proportions. The change from baseline (e.g. for HbA1c, FBG levels etc) will be analysed using the general linear model and the baseline visits of the respective parameter will be considered as covariate. The rates

of hypoglycemia will be analysed using the Negative Binomial Model without categorical variable i.e. the generalized linear model and the baseline visit of HbA1c will be considered as covariate.

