17.2 Analysis

Population: FAS and PPS

Stratification: Table: By visit

Listing: By subject, visit and each laboratory test parameter

Statistics: Summaries of all the clinical laboratory tests (haematology, clinical chemistry and urinalysis) will include descriptive statistics of the following:

- Actual and change from baseline (n, mean, standard deviation, standard error median, minimum, maximum) (for quantitative measurements)
- Frequencies and percentages (n and %) (for qualitative measurements)

Continuous clinical laboratory chemistry and haematology measures will be summarized as change from screening visit (Week -2) to Week 24 using the general linear model, with the change from

week -2 to week 24 in respective laboratory parameter as dependent variable and the screening visit (Week -2) value of the respective response variable as covariate.

Missing data imputation will be performed as mentioned in section 8.2 point 5.

Efficacy tables will be presented for with and without imputed values separately for each population set.

The estimate, 95% confidence interval and p-value will be summarised for efficacy table.

The regression line for the general linear model without categorical variable is as follows:

 $Y = \alpha + \beta (X)$

Where,

Y= The response change in respective laboratory parameter.

 $\alpha = Intercept$

β =slope

X= Covariate i.e. Baseline (i.e. week -2) respective laboratory parameter

The hypothesis is as follows

H0: $\beta = 0$

i.e. There is no statistically significant change in respective laboratory parameter at week 24 from screening visit (Week -2) depending on the Baseline (i.e. week -2) respective laboratory parameter.

V/s

H1: β ≠ 0

i.e. There is statistically significant change in respective laboratory parameter at week 24 from screening visit (Week -2) depending on the Baseline (i.e. week -2) respective laboratory parameter.

The above hypothesis will be tested based on α (alpha)=0.05, if the p-value \geq 0.05 then we will conclude that there is no statistically significant change in respective laboratory parameter at week 24 from screening visit (Week -2) i.e. Ho is accepted.

Page 49 of 85

The sample SAS programme is as follows:

proc mixed data=dataset;

model Y= X / s cl;

estimate "Model with Mean baseline lab parameter" int 1 lab parameter baseline mean /CL;

ods output estimates=output dataset;

run;

quit;

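### The SAP attaches an accept-or-reject rule at alpha = 0.05 to about 72 distinct safety and secondary tests, with no multiplicity control and no exploratory label, in a trial whose primary analysis is estimation only

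*SAP*

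**What the plan says.** The primary analysis (SAP 19.2.1) is the percentage of subjects with at least one hypoglycaemic event to Week 24, with an exact 95% confidence interval and no test. Protocol 5.2 and 10.1 base the sample size on the regulator's minimum of 200 subjects and on confidence-interval precision.

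The other analyses are framed as tests. SAP 17.2, 18.2, 20.2.2, 20.2.4, 20.2.6, 20.2.8, 20.2.11 and 20.2.12 each state a null and an alternative for the slope on baseline, a 0.05 level, and the conclusion to draw; 20.2.3 takes over the rule of 20.2.2 by reference. For HbA1c the SAP says "The above hypothesis will be tested based on α (alpha)=0.05" and, if p is 0.05 or more, "then we will conclude that there is no statistically significant change in HbA1c levels at week 12 and 24 from baseline", the null being accepted. The protocol sets the general level in 10.3.1: "All tests of treatment effects will be conducted at a 2-sided alpha level of 0.05, unless otherwise stated". The laboratory section asks for the same output: "The estimate, 95% confidence interval and p-value will be summarised for efficacy table".

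SAP 20.2.4 adds that "efficacy tables will be presented for with and without imputed values separately for each population set", and similar wording appears for the other linear models. SAP 7.4 states "This is the single arm study so no comparison tests will be performed" and then lists the models.

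**The concern.** Followed as written, the report would give a verdict on each laboratory parameter, vital sign, glucose point, visit and questionnaire domain at an unadjusted 5% level. Nothing in the design supports formal conclusions of that kind: no power, effect size or success criterion is attached to any of these tests. In a safety study the risk runs both ways. Chance laboratory or vital-sign results can be reported as changes, and a p-value of 0.05 or more is turned into a statement of no change. The protocol uses the word exploratory only for additional analyses beyond the planned ones, so it does not cover these tests.

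**Working it through.** **The plan's own figures.** The documents state no number of tests and no family-wise error rate, so there is none to reproduce. The figures behind the sample size do reproduce: 200/0.80 = 250 enrolled; 250/0.85 = 294.1, rounded up to 295 screened; and 1.96 × √(0.11 × 0.89/250) = 3.9%, as in Table ABEX.3. The size is set by completers and precision, not by any of these tests.

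**Counting the tests (one population, one imputation version).**

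| Source | Tests |
|---|---|
| Laboratory, SAP 17.1–17.2: 12 haematology + 15 chemistry | 27 |
| Vital signs, SAP 18 | 3 |
| *Safety subtotal* | *30* |
| HbA1c, 20.2.4: Weeks 12 and 24 | 2 |
| SMBG, 20.2.8: 7 points × 3 visits | 21 |
| Weight, BMI, percentage weight change, 20.2.11 | 3 |
| ITSQ, 20.2.12: 5 domains + overall | 6 |
| Hypoglycaemia rates, 20.2.2–20.2.3: 5 types × 2 periods | 10 |
| *Secondary-endpoint subtotal* | *42* |
| **Total** | **72** |

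The chemistry and urinalysis headings are swapped in SAP 17.1, so the laboratory count follows protocol Appendix 2. The three FBG tests of 20.2.6 are left out because the SAP itself says they give the same results as pre-breakfast SMBG; with them the count is 75. The per-30-day and per-year rates share one slope test and are counted once. SMBG is counted at Weeks 4, 8 and 12, where 20.2.8 places the model; its hypothesis text also names Week 24, which would add 7. Across these readings the total runs from 71 to 82.

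**Number of p-values.** The 62 linear-model tests appear in two populations, with and without imputation; the 10 rate tests appear in two populations: 62 × 4 + 10 × 2 = 268. With FBG included: 65 × 4 + 10 × 2 = 280. These are far from independent.

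**Error rate for the family where no change is a plausible truth.** Take the 30 laboratory and vital-sign tests, assume no true mean change, and assume that the p-value is the one for mean change.

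- Independent tests: 1 − 0.95^30 = 0.785, or 79%.
- Equicorrelated normal statistics: 1 − P(all |Z| < 1.96), by numerical integration, gives 51% at correlation 0.5 and 17% at 0.9.
- Expected false positives: 30 × 0.05 = 1.5, whatever the correlation.

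The correlation is an assumption; neither document gives one.

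**Why the figures stop there.** The written null concerns the slope: "There is no statistically significant change in HbA1c levels at week 12 and 24 from baseline depending on the baseline HbA1c". The sample code estimates something else, the mean change at the mean baseline ("int 1 HbA1c_baseline mean /CL"). In simulations with no true mean change and equal variances, at n = 200 and 250, the slope null was rejected in 100% of trials when the baseline-to-Week-24 correlation was 0.3 to 0.7, in over 99% at 0.8, in 89–95% at 0.9 and in 61–71% at 0.95. With a real uniform fall of 1 SD unrelated to baseline (n = 200), it was rejected in only 5%. The per-test error of the rule as written is therefore not 5%, and a family-wise calculation based on 5% does not describe it.

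**Ranking of versions.** Protocol 10.3.1 places the analyses on the FAS or safety set, and 10.3.2–10.3.4 repeat them in the PPS. Protocol 10.3.2.3, 10.3.3.3 and 10.3.4 tie the linear models for vital signs, SMBG, weight/BMI and ITSQ to LOCF data. The SAP lists FAS and PPS side by side and does not carry this ranking over. For the HbA1c, FBG and laboratory models, neither document says which imputation version is the main one.

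**The case against.** The strongest reply is that little depends on these tests. The primary result is an interval estimate, no success criterion uses a secondary p-value, and many readers would treat such p-values as descriptive anyway. That limits the consequence and stands. It does not remove the rule, which the SAP states explicitly in eight sections.

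Several stronger readings are tempting, and the documents do not support them:

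- **About 75 distinct secondary tests.** Thirty are safety summaries outside the secondary endpoint list in SAP 3.2, and three are declared duplicates.
- **A near-certain false positive across the whole set.** Independence over all 75 tests would give 98%, and correlation 0.5 would give 71%. Both need every null to be true, which is unrealistic for HbA1c, FBG and SMBG in inadequately controlled subjects starting titrated insulin. Nor do they hold whichever p-value is used: the slope null fails as shown above, and for the rate models the estimate in the sample code would test a rate of one event per time unit, which is not a null of no effect.
- **No version is named as main.** That is true of the SAP read alone. The protocol ranks FAS above PPS and specifies LOCF for several models.
- **SAP 7.4 contradicts the rest of the plan.** Its stated reason is the single arm, so the natural meaning is that no groups are compared. It needs clarifying and is not a proven contradiction.
- **The report must declare significant changes.** Only the conclusion for p of 0.05 or more is written out; the opposite conclusion is implied by the alternative hypothesis.

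**Conclusion.** The concern holds as a labelling and decision-rule defect. A formal 0.05 rule is attached to about 72 distinct safety and secondary tests (71 to 82 by reading, the upper end including the FBG duplicates), with no multiplicity control and no exploratory label, in a design built for estimation. The defensible size is for the 30 laboratory and vital-sign tests: a 51% chance of at least one false significant change at correlation 0.5, ranging from 79% at 0 to 17% at 0.9. This assumes that the mean-change p-value is used and that there is no true change. The slope hypothesis is a separate defect which a multiplicity adjustment would not cure. The open question on versions is narrow: the SAP omits the protocol's ranking, and the main imputation version is unnamed for HbA1c, FBG and laboratory data. The primary result is unaffected.

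**What to change.** 1. Delete the null/alternative statements and the conclusion rules in SAP 17.2, 18.2, 20.2.2, 20.2.4, 20.2.6, 20.2.8, 20.2.11 and 20.2.12 (which also settles 20.2.3), and report estimates with 95% confidence intervals. This removes the slope hypothesis as well. If a p-value column is kept, say which quantity it refers to.
2. In SAP 7.4, state that the only primary result is the FAS incidence of total hypoglycaemia to Week 24 with its 95% confidence interval; that all other p-values and intervals are nominal, unadjusted and support no confirmatory conclusion; and that the sentence on comparison tests means no between-group tests.
3. Carry the protocol's ranking (FAS main, PPS a repeat) into the SAP, and name one main imputation version for the HbA1c, FBG and laboratory models.

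The cost is SAP wording and table shells; no data, visits or subjects are added. The downside is that the sponsor can no longer call individual secondary or safety changes statistically significant as formal conclusions.

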18.2 Analysis

| Population: | FAS and PPS |
|-----------------|---------------------|
| Stratification: | Table: By visit |
| | Listing: By subject |

Statistics: Descriptive statistics (n, mean, standard deviation, standard error, median, minimum, maximum) will be calculated for all the vital signs variables (Actual and change from baseline) for table. Listing will be presented for all the vital signs parameter by subject.

> The change from baseline values to Week 24 will be analysed using the general linear model, with the baseline value of the response variable as covariate after applying the LOCF method to missing values.

> Missing data imputation will be performed as mentioned in section 8.2 point 1.

Efficacy tables will be presented for with and without imputed values separately for each population.

The estimate, 95% confidence interval and p-value will be summarised for efficacy table.

The regression line for the general linear model without categorical variable is as follows:

 $Y = \alpha + \beta (X)$

Where,

Y= The response change in respective vital signs parameter.

 $\alpha = Intercept$

 $\beta = slope$

X= Covariate i.e. Baseline of respective vital signs parameter The hypothesis is as follows

H0: $\beta = 0$

i.e. There is no statistically significant change in respective vital signs parameter at week 24 from baseline depending on the Baseline of respective vital signs parameter.

V/s

H1: β ≠ 0

i.e. There is statistically significant change in respective vital signs parameter at week 24 from baseline depending on the Baseline of respective vital signs parameter.

The above hypothesis will be tested based on α (alpha)=0.05, if the p-value \geq 0.05 then we will conclude that there is no statistically significant change in respective vital signs parameter at week 24 from baseline i.e. Ho is accepted.

The sample SAS programme is as follows:

proc mixed data=dataset;

model Y= X / s cl;

estimate "Model with Mean of baseline respective vital signs parameter " int 1 vital signs parameter baseline mean /CL;

ods output estimates=output dataset;

run; quit;

19. Primary efficacy assessments

The primary endpoint parameter is mention below

- 19.1 Variables and derivations
- 19.1.1 Incidence of total (symptomatic or asymptomatic with FBG level of ≤54 mg/dL [≤3.0 mmol/L]) hypoglycaemic events at Week 24

Variables:

- What was the blood glucose level (mg/dL) prior to treating the event? (In eCRF "Hypoglycemia Events" form)

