20.2 Analyses

- 20.2.1 Serious adverse events (SAEs) and treatment-emergent adverse events (TEAEs)
 - Population: FAS and PPS Stratification: Table: NA Listing: NA Statistics: The SAE and TEAE will be identified by using derivation mentioned in section 20.1.1. Summary statistics for SAEs and TEAEs will be presented as frequency and percentage (n and %) for table.

20.2.2 Rates per 30 days and per subject year of total hypoglycemic events (symptomatic or asymptomatic)

| Population: | FAS and PPS |
|-------------|-------------|
|-------------|-------------|

Stratification: Table: NA

Listing: NA

Statistics: The rate that is the number of hypoglycemic events per subject over the study period i.e. Day 0 to week 24/week 28 will be summarised as continuous variables as (n, mean, standard deviation, standard error, median, minimum, maximum).

> By using the formula mentioned in section 20.1.2, we will get the Rates per 30 days and per subject year (365.25 days) between two time points (i.e. baseline to end of treatment/study) and This Rates per 30 days and per subject year (365.25 days) will be summarised as (n, mean, standard deviation, standard error, median, minimum, maximum).

> Summary statistics and efficacy table will be presented separately for baseline to end of treatment and baseline to end of the study.

Page 63 of 85

The Negative Binomial Model without categorical variable i.e. the generalized linear model will be used with HbA1c as covariate and the log of the study treatment exposure time as offset variable.

The estimate, 95% confidence interval and p-value will be provided for efficacy table.

The Negative binomial regression equation is as follows:

Y = Offset variable + α + β (X)

Where,

Y= The response rate of 30 days and per subject year for total hypoglycaemic events.

Offset variable = The log of study treatment exposure time for rates per 30 days and per subject year (See section 20.1.2 for formula)

 $\alpha = Intercept$

 β =slope

X= Covariate i.e. Baseline HbA1c results

The hypothesis is as follows

H0: $\beta = 0$

i.e. The Rate of per 30 days and per subject year of total hypoglycaemic events not significantly differs depending on the Baseline HbA1c..

V/s

H1: β ≠ 0

i.e. The Rate of per 30 days and per subject year of total hypoglycaemic events significantly differs depending on the Baseline HbA1c. events.

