The above hypothesis will be tested based on α (alpha)=0.05, if the p-value \geq 0.05 then we will conclude that there is no statistically significant change in rates per 30 days and per subject year of total hypoglycaemic events. i.e. Ho is accepted. The sample SAS programme is as follows for negative binomial model:

proc genmod data=Dataset;

model Response Rate=Baseline_HbA1c / cl dist=NB link=log offset= offset variable;

estimate "Model with Mean baseline HbA1C for rate per 30 days and per year" int 1 Baseline HbA1c observed mean / exp;

ods output estimates=Output dataset;

run;

quit;

20.2.3 Incidence and rates per 30 days and per subject-year of nocturnal, severe, documented symptomatic and asymptomatic hypoglycemic events

Population: FAS and PPS

Stratification: Table: NA

Listing: NA

Statistics: By using the formula mentioned in section 20.1.2, we will get the Rates per 30 days and per subject year (365.25 days) between two time points (i.e. baseline to end of treatment/study) for each hypoglycaemic events category separately.

> The incidence and rates per 30 days and per subject-year for each below mentioned hypoglycemic events will be analysed similarly as mentioned in section 19.2.1 for incidence and section 20.2.2 for rates of hypoglycemic events.

- Nocturnal hypoglycemia
- Severe hypoglycemia
- Documented symptomatic hypoglycemia, and
- Asymptomatic hypoglycemia

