20.2.6 Change in FBG levels at Weeks 4, 8, and 12 from baseline

Population: FAS and PPS

Stratification: Table: NA

Listing: By Subject

Statistics: The actual and change from baseline data of FBG levels will be summarised as (n, mean, standard deviation, standard error, median, minimum, maximum and number with missing values) and the listing will be presented.

The change from baseline of FBG level variable will be calculated by using formula mentioned in section 20.1.6.

The change from baseline variable and the missing FBG results imputation i.e. LOCF will be done by using derivations mentioned in section 20.1.6 and the efficacy tables will be presented for with and without imputed values separately for each population set.

The change in FBG level from baseline to Week 4,8 and 12 will be analysed using the general linear model.

The change from baseline in FBG level as dependent variable and the baseline value of FBG level as covariate.

The estimate, 95% confidence interval and p-value will be summarised for efficacy table.

The regression line for the general linear model without categorical variable is as follows:

 $Y = \alpha + \beta (X)$

Page 68 of 85

Where,

Y= The response change in FBG levels.

 $\alpha = Intercept$

```
\beta = slope
```

X= Covariate i.e. Baseline FBG results

The hypothesis is as follows

H0: $\beta = 0$

i.e. There is no statistically significant change in FBG levels at Week 4,8 and 12 from baseline depending on the baseline FBG level.

V/s

H1: β ≠ 0

i.e. There is statistically significant change in FBG levels at Week 4,8 and 12 from baseline depending on the baseline FBG level.

The above hypothesis will be tested based on α (alpha)=0.05, if the p-value \geq 0.05 then we will conclude that there is no statistically significant change in FBG levels at Week 4,8 and 12 from baseline i.e. Ho is accepted.

The sample SAS programme is as follows:

proc mixed data=dataset;

model Y= X / s cl;

estimate "Model with Mean baseline FBG" int 1 FBG baseline variable mean /CL;

ods output estimates=output dataset;

run;

quit;

Note: For the Change from FBG levels endpoint we are using the "7-point SMBG levels blood glucose parameter i.e. "Blood glucose concentration (mg/dL) upon awakening before breakfast (Fasting)" also, we have change form 7-point SMBG level endpoints (See section 20.2.8) i.e. we will get same results from both parameters.

20.2.7 Self-monitored 7-point SMBG levels at baseline, Weeks 4, 8, 12, and 24

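### The SAP tests the slope on baseline but concludes about change from baseline, and its sample code tests a third way; for hypoglycemia rates neither p-value supports the conclusion

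*SAP*

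**What the plan says.** SAP sections 17.2 (laboratory), 18.2 (vital signs), 20.2.4 (HbA1c), 20.2.6 (FBG), 20.2.8 (7-point SMBG), 20.2.11 (weight and BMI) and 20.2.12 (ITSQ) share one template:

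- **Model.** Y = α + βX, where Y is the change and X the baseline value (Week 4 for ITSQ).
- **Null hypothesis.** β = 0. The verbal gloss in 18.2 opens "There is no statistically significant change in respective vital signs parameter at week 24 from baseline" and in 20.2.6 "There is no statistically significant change in FBG levels at Week 4,8 and 12 from baseline", and each then adds that this is as a function of the baseline value.
- **Decision rule.** That hypothesis is tested at 0.05. The conclusion at p ≥ 0.05 drops the qualifier about baseline. For HbA1c: "then we will conclude that there is no statistically significant change in HbA1c levels at week 12 and 24 from baseline". No rule is written for p < 0.05.
- **Sample code.** A PROC MIXED ESTIMATE statement puts coefficient 1 on the intercept and the mean baseline on the covariate. Only that result is kept: "ods output estimates=output dataset".
- **Table.** "The estimate, 95% confidence interval and p-value will be summarised for efficacy table". The source of the p-value is not named.

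Section 20.2.2 (hypoglycemia rates, extended to the event subtypes by 20.2.3) uses the same pattern in a negative binomial model with baseline HbA1c as covariate and log exposure as offset. The response is defined as "Y= The response rate of 30 days and per subject year for total hypoglycaemic events", and the conclusion at p ≥ 0.05 is that "there is no statistically significant change in rates per 30 days and per subject year of total hypoglycaemic events". Section 7.4 says that no comparison tests will be done and names no tested quantity.

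**The concern.** The slope answers whether subjects with higher baseline values change more than those with lower ones. It does not answer whether subjects changed. Under the written rule, a fall that is much the same in everyone gives a non-significant slope and would be reported as no change. Conversely, regression to the mean produces a negative slope in repeated glucose, laboratory and blood pressure values even when the mean does not move. Under the reading that H1 implies, that would be reported as a change.

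The decision rule points to the slope p-value and the code to the ESTIMATE p-value, so two programmers working from the same SAP could fill the same cell differently.

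For rates there is no baseline rate in the model, so a statement about change in rates has no basis in either p-value.

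**Working it through.** The plan gives no figure for this point to reproduce. The only documented inputs are n and the 0.05 level: Protocol 10.1 has 250 enrolled and 20% drop-out, 250 × 0.80 = 200 completers. All SDs, slopes, correlations, mean changes, event rates and dispersions below are assumptions.

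**1. What each p-value tests (linear models).** The slope test is of β = 0. The ESTIMATE test is of α + β·x̄ = 0. In least squares with an intercept, the fitted value at x̄ equals ȳ, so ESTIMATE is the mean change when x̄ is the mean of the analysed subjects. These are different hypotheses.

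**2. Real change, read through the slope.** The slope test has noncentrality δ = |β|·SD(X)·√n / residual SD. With n = 200 and both SDs 1, β = −0.1 gives δ = 0.1 × 14.14 = 1.41, so the chance of p ≥ 0.05 is about Φ(1.96 − 1.41) = 0.71. With equal SDs at both visits, β = ρ − 1 and δ = √[n(1 − ρ)/(1 + ρ)]; at ρ = 0.9, δ = √(200 × 0.1/1.9) = 3.24 and the chance is about Φ(1.96 − 3.24) = 0.10. Simulation (20,000 trials per row, true mean change −1.2):

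| Assumption | Slope p ≥ 0.05 (read as no change) | ESTIMATE p < 0.05 |
|---|---|---|
| Equal SDs, ρ = 0.95 | 39.1% | 100% |
| Equal SDs, ρ = 0.9 | 10.7% | 100% |
| Equal SDs, ρ = 0.8 | 0.4% | 100% |
| Equal SDs, ρ ≤ 0.7 | about 0% | 100% |
| Residual SD 1, β = 0 | 95.1% | 100% |
| Residual SD 1, β = −0.1 | 70.6% | 100% |
| Residual SD 1, β = −0.2 | 20.1% | 100% |
| Residual SD 1, β = −0.3 | 1.3% | 100% |

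At β = 0 and residual SD 1 the implied Week 24 SD is √(1 + 1) = 1.41, against 1 at baseline.

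**3. No true mean change, equal SDs.**

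| ρ | Slope p < 0.05 | ESTIMATE p < 0.05 |
|---|---|---|
| 0.95 | 61.3% | 5.2% |
| 0.9 | 89.2% | 5.9% |
| 0.8 | 99.5% | 6.5% |
| 0.7 | 100% | 7.4% |
| 0.5 | 100% | 8.9% |

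The ESTIMATE test exceeds 5% because the model treats x̄ as fixed. The true variance of the mean change is 2(1 − ρ)SD²/n and the model uses (1 − ρ²)SD²/n, a ratio of 2/(1 + ρ). At ρ = 0.5 the SE is short by a factor √1.333 = 1.155; 1.96/1.155 = 1.70, which gives about 9%.

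A separate run (4,000 trials, n = 200, residual SD 1) agrees: mean change −1.0 with slope 0, slope test 4.8% and ESTIMATE 100% significant; mean change 0 with slope −0.3, 98.8% and 6.1%. At mean change −1.0 with slope −0.5 both reject in 100%, so the tests do not always disagree.

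**4. Rates.** With a count response and offset log(exposure/unit), the ESTIMATE p-value tests log rate = 0, that is, exactly one event per unit. Simulation: n = 200, 168 days, 300 to 400 trials, assumed known dispersion. At a true rate of 1 per year, p < 0.05 occurred in 3% to 5% of trials with the year as unit and in 100% with 30 days as unit, on the same data. At 12.175 per year (365.25/30, or one per 30 days) the figures were 100% and 6%. The slope p-value tests association with baseline HbA1c. Neither is a test of change.

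**5. Rate response with an offset.** If the response is already a rate and the offset is also applied, exposure is divided out twice. At 168 days the fitted 30-day rate is the true rate divided by 168/30 = 5.6, and the fitted yearly rate is the true rate times 365.25/168 = 2.17.

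**The case against.** The code saves only the ESTIMATE table, which gives an estimate, an interval and a p-value in one row, so a programmer who follows it reports the right test. On this view the conclusion merely dropped a qualifier. It is true that the code gives a usable route. But it is labelled a sample, while the decision rule explicitly ties the p-value to the slope hypothesis, so the two conflict and no sentence settles it.

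The largest false no-change figures need a spread that rises by 41% by Week 24. With equal SDs the problem is confined to high correlations, and the HbA1c entry range (Protocol 6.1, at least 7.0% and below 11.0%) favours a negative slope. This is correct, and it limits that half of the concern. It strengthens the other half, since a slope driven by regression to the mean is what would be significant without any mean change. That half does rest on an inferred reading, because no p < 0.05 rule is written.

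The offsets in 20.2.1 to 20.2.3's derivations suit a count response, so the double adjustment arises only if the definition of Y and the sample code are taken literally. That stands as a condition.

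Finally, the consequence is limited: no success criterion uses these p-values, and means with SD and SE are tabulated alongside.

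**Conclusion.** The concern holds. In seven sections the stated null does not support the stated conclusion and does not match the sample code. In 20.2.2, and 20.2.3 by reference, the conclusion follows from neither available p-value.

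The size depends on slopes and correlations that the documents do not give. A real change is missed mainly when the slope is near zero or the correlation very high. A spurious finding of change is likely over the whole range examined if a significant slope is read as H1 implies. If the ESTIMATE output is used, the conclusion on mean change is approximately valid, with a type I error of 5% to 9% in these scenarios.

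The harm is a wrong significance statement in secondary and supportive analyses, not a hidden estimate, except that a literal rate-plus-offset model would also give wrong rates. The primary incidence with its Clopper-Pearson interval, basal insulin dose and intrasubject variability are not affected. It should be fixed before the analysis is programmed.

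**What to change.** In 17.2, 18.2, 20.2.4, 20.2.6, 20.2.8, 20.2.11 and 20.2.12:

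- Restate H0 as baseline-adjusted mean change, α + β·mean baseline, equal to zero (Week 4 mean for ITSQ).
- State that the tabulated estimate, interval and p-value come from the ESTIMATE statement.
- Say that H0 is not rejected, rather than accepted.
- Note that this test treats the mean baseline as fixed and can be somewhat liberal; the SE of the mean change in the descriptive table serves as a check.

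In 20.2.2 and 20.2.3, delete the hypothesis and the conclusion about change. Report the estimated rate with its 95% confidence interval only, and specify the event count as the response with the log-exposure offset.

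In 7.4, name the quantity that is tested.

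The cost is wording in the seven sections and 7.4, plus deleting the rate test and naming the event count as the response in the sample PROC GENMOD code. The linear-model code can stay as it is, and no data collection changes.
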